#### Sensitivity analysis of the secondary continuous estimand ('treatment policy')

As for the primary analysis of this estimand, the sensitivity analysis will also have the general rule applied if there are not enough observed data to facilitate MI of data. Since the MI in this sensitivity analysis applies a copy-reference approach, only the discontinued/non-discontinued subjects randomised to placebo are applicable for this. The rule will, again, be that if there are 2 or less observed values at the analysed visit in the respective placebo group

Trial ID: LP0162-1346	Date: 21-OCT-2020	Version: v1.0 Page 15 of 35
-----------------------	-------------------	--------------------------------

then missing data within the group will be imputed using the worst observation carried forward.

In the multiple imputation methods specified, the variables used in the imputation procedures will not be prior CSA use and baseline IGA, but prior CSA use, county (Germany Yes/No), and baseline IGA.

#### Primary analysis of the tertiary estimand (COVID-19 modified composite)

In the multiple imputation methods specified, the variables used in the imputation procedures will not be prior CSA use and baseline IGA, but prior CSA use, county (Germany Yes/No), and baseline IGA.

#### SCORAD

For the calculation of SCORAD, the protocol states that dryness is evaluated on uninvolved areas. This means that if a subject has an extent of 100% then there is no area to score. In the event that dryness is missing and extent is 100% then 0 (none/absent) will be imputed instead.

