11.2.4 Body surface area involvement

The total body surface area (BSA) affected by AD will be assessed by the investigator for each section of the body as component A of SCORAD (see Section 11.3.3) and will be reported as a percentage of all major body sections combined. The following body regions will be assessed (brackets show the highest possible score for each region): head and neck (9%), anterior trunk (18%), back (18%), upper limbs (18%), lower limbs (36%), and genitals (1%). The total BSA score will be assessed according to the schedule of trial procedures (Section 4).

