11.3.3 SCORing Atopic Dermatitis

The SCORAD is a validated tool to evaluate the extent and severity of AD lesions, along with subjective symptoms (28). The maximum total score is 103, with higher values indicating more severe disease. SCORAD will be assessed according to the schedule of trial procedures (Section 4).

The assessment will be based on the condition of the disease at the time of evaluation and not in relation to the condition at a previous visit. Whenever possible, SCORAD should be assessed by the same investigator at each visit to reduce inter-rater variability.

The assessment consists of 3 components: A = extent, B = intensity, and C = subjective symptoms.

Extent (A)

The extent of AD is assessed as a percentage of each defined body area and reported as the sum of all areas (maximum score = 100%)

Intensity (B)

The intensity of 6 specific symptoms of AD (erythema, oedema/papulation, oozing/crusting, excoriation, lichenification, and dryness) is assessed by the investigator on an average representative area using the following scale:

0	=	None/absent
1	=	Mild
2	=	Moderate
3	=	Severe

Note: dryness is evaluated on uninvolved areas.

The sum of intensity score of the 6 symptoms will be reported (maximum score = 18).

Subjective symptoms (C)

A subjective assessment of the average itch and sleeplessness over the last 3 days/nights is recorded for each symptom by the subject on a visual analogue scale, where 0 is no itch (or sleeplessness) and 10 is the worst imaginable itch (or sleeplessness), with a maximum possible score of 20.

The SCORAD is calculated as: $A/5+7B/2+C$

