14.3.9.1 Primary estimand for the continuous secondary endpoints: ‘hypothetical’

The primary estimand for the continuous secondary endpoints will be:

- Treatment difference in change from baseline to Week 16/ Week 26 in SCORAD and DLQI scores, respectively, if all subjects adhered to the treatment regimen in the sense that they did not discontinue IMP permanently, no rescue treatment was made available, and as if the COVID-19 pandemic did not happen before Week 16/ Week 26.

The primary estimand assesses the expected benefit when adhering to the treatment regimen tralokinumab+TCS with no rescue treatment or subject-onset of the COVID-19 pandemic as compared to a treatment regimen with placebo+TCS with no rescue treatment or subject-onset of the COVID-19 pandemic.

Primary analysis of the primary estimand (continuous secondary endpoints)

Data collected after permanent discontinuation of IMP, after initiation of rescue treatment, or after subject-onset of the COVID-19 pandemic will not be included in the analysis (Panel 13).

The endpoints will be analysed using a repeated measurements model on the post-baseline responses up to Week 26 with an unstructured covariance matrix, Kenward-Roger approximation to estimate denominator degrees of freedom, and the mean modelled as follows (shown for change from baseline in SCORAD):

Change from baseline in SCORAD

$$= \text{treatment} \times \text{visit} + \text{baseline SCORAD} \times \text{visit} + \text{prior CSA use} + \text{country} + \text{baseline IGA}$$

This model assumes that data is MAR within each treatment group. The estimates will be presented with nominal p-values and 95% CI at each visit. The comparisons between tralokinumab+TCS and placebo+TCS will be at Week 16 and Week 26.

Sensitivity analysis for the primary estimand (continuous secondary endpoints)

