14.3.16 General principles

Unless otherwise stated, all significance tests will be 2-sided using the 5% significance level. All CIs will be presented with 95% degree of confidence. An observed-cases approach will be used for tabulations of data by visit (i.e. involving only those subjects who attended each specific visit).

Categorical data will be summarised using the number and percentage of subjects in each category and treatment group. Continuous data will be summarised using the mean, median, standard deviation, 1st quartile, 3rd quartile, minimum, and maximum values.

All the analyses specified in the protocol will be reviewed in relation to the blinded data actually obtained and the statistical analysis plan and the analysis set definition document will be finalised before breaking the randomisation code.

Any changes from the statistical analysis planned in this clinical trial protocol will be described and justified in a protocol amendment, the statistical analysis plan, and/or in the CTR dependent on the type of deviation.

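### Does scoring unassessable dryness as 0 at 100% extent distort SCORAD enough to call for a different rule?

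*SAP*

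**What the plan says.** Protocol 11.3.3 defines SCORAD as A/5 + 7B/2 + C. A is extent (up to 100%), B is the sum of six intensity items graded 0 to 3 (up to 18), and C is the two subjective symptoms (up to 20). It adds: "The maximum total score is 103, with higher values indicating more severe disease". Dryness is one of the six B items, but it is graded in a different place from the others: "Note: dryness is evaluated on uninvolved areas".

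SAP 6.6.3.2, under SCORAD, observes that a subject with full extent has nowhere to grade dryness, and then sets the rule: "In the event that dryness is missing and extent is 100% then 0 (none/absent) will be imputed instead". Both conditions must hold. A dryness grade that a site did record at 100% extent is left alone.

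Change in SCORAD at Weeks 16 and 26 are secondary endpoints (Protocol 6) and are tested hierarchically (Protocol 14.3.6). Under the tested estimand in Protocol 14.3.9.1, data collected after permanent discontinuation of IMP, after the start of rescue treatment, "or after subject-onset of the COVID-19 pandemic will not be included in the analysis".

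**The concern.** The SAP explains why the item is blank, but not why a blank should count as no dryness. Zero is the bottom of the item's range, so if these subjects have any meaningful dryness grade, the rule can only err towards milder disease, and it does so only at maximal extent. It also breaks the expected ordering: a subject whose extent worsens to 100% with every other sign unchanged can receive a lower SCORAD.

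At stake are two endpoints in the testing hierarchy, with baseline SCORAD also a covariate in their model. If the rule applies at baseline only, improvement is understated. If it applies after baseline only, improvement is overstated. If the two arms had different numbers of such records, the treatment difference would move.

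**Working it through.** **Inputs.** The formula and item ranges come from Protocol 11.3.3, the rule from SAP 6.6.3.2, and 250 subjects randomised 1:1 (125 per arm) from Protocol 7.2. The documents do not give the number of affected records or the distribution of dryness grades, so both are assumptions below.

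**1. The stated maximum.** 100/5 + 7×18/2 + 20 = 20 + 63 + 20 = 103, as the protocol says.

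**2. Ceiling when the rule applies.** With dryness 0, B is at most 15: 20 + 52.5 + 20 = 92.5, which is 10.5 below 103. For an assumed dryness grade d, the record is 3.5d lower than if d had been entered: 3.5, 7.0 or 10.5 points for d = 1, 2, 3.

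**3. Ordering.** At 99% extent with all else maximal, SCORAD is 19.8 + 63 + 20 = 102.8, so reaching 100% under the rule gives a fall of 10.3 (6.8 and 3.3 for prior dryness 2 and 1). In general the score falls if (100 − A)/5 < 3.5d, that is, if prior extent A exceeded 82.5%, 65% or 47.5% for d = 1, 2, 3. This holds every other item fixed while extent rises to 100%. That is an algebraic property of the score, not a likely clinical course.

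**4. Is the alternative better?** Proration sets B to 6/5 of the sum of the five graded items, which fills dryness with their mean m. If a latent grade d is supposed to exist, the mean absolute error is 3.5×E|d| under the 0 rule and 3.5×E|d − m| under proration.

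With d equally likely to be 0, 1, 2 or 3:

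| Other items average | 0 rule | Proration |
|---|---|---|
| 1 | 5.25 | 3.5 |
| 2 | 5.25 | 3.5 |
| 3 | 5.25 | 5.25 |

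Now let p be the share with dryness 0 and spread the rest evenly over 1 to 3. Under the 0 rule, E|d| = 2(1 − p). Setting this equal to the proration value gives the break-even:

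- m = 1: 2(1 − p) = 1, so p = 0.50.
- m = 2: 2(1 − p) = 2p + (2/3)(1 − p), so p = 0.40.
- m = 3: 2(1 − p) = 3p + (1 − p), so p = 0.25.

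Above these shares the 0 rule has the smaller error. With m = 2, the errors run from 7.0 (0 rule) against 2.33 (proration) at p = 0 to 2.1 against 5.6 at p = 0.7. Proration also leaves jumps from 99% to 100% extent of 0.2 + 3.5(m − d): down 3.3 for m = 2, d = 3, and up 10.7 for m = 3, d = 0. The upward jump is larger than the 10.3 fall in step 3.

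**5. Effect on the treatment comparison.** One affected post-baseline record moves an arm mean by at most 10.5/125 = 0.084 points, or 10.5/100 = 0.105 if only 100 subjects contribute. An assumed net excess of 1 to 8 cases in one arm shifts the difference by 3.5/125 = 0.028 to 8×10.5/125 = 0.672 points, in either direction. The top figure needs eight excess cases, all with assumed dryness 3. Two features reduce the effect. A subject affected at both baseline and the analysed visit, with the same latent grade, has it removed from both scores, so the change is unaltered. A baseline-only case reaches the adjusted difference through the baseline slope, because the model includes baseline SCORAD by visit.

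**The case for a change.** The best case for changing the rule is that 0 is the mildest grade and is given without a reason, while the SAP already has a neutral method elsewhere: Table 2 of SAP 6.6.5 fills a single missing HADS question with the mean of the others in its subscale. SAP 6.6.8 takes the conservative value for missing tube weights. Xerosis is among the minor diagnostic features of atopic dermatitis in Protocol Appendix 4, which makes absence an odd default. A second scoring would cost a line of code and a short table.

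Part of this stands. The choice of 0 is unexplained, and affected records do have a lower ceiling. But the HADS analogy is weak. Those questions are of one kind, whereas dryness is graded on uninvolved skin and the other five items are signs of the eczema itself. The 103 benchmark is also less firm than it looks, because reaching it takes 100% extent together with dryness 3 on skin that, read literally, does not exist. With no uninvolved skin, recording its dryness as absent is a defensible literal reading.

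The rule also has a benefit. Without some fill-in, a blank dryness item would presumably leave SCORAD incomplete, and SAP 6.8.1 excludes subjects with a missing baseline from change-from-baseline analyses. The rule keeps the subjects with the most extensive disease in the analysis.

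**Conclusion.** This is a fair trade-off, and no change is called for. The rule is an unexplained convention for an item without a defined value at full extent. It is not a demonstrated bias. Proration ties with it at 5.25 when the other items are at 3, does worse once dryness 0 is common, and has its own discontinuities, so reasonable statisticians would differ.

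The likely effect is negligible. The trigger needs every region in Protocol 11.2.4 fully involved (9 + 18 + 18 + 18 + 36 + 1 = 100) and a blank dryness item. The tested estimand discards data after intercurrent events, which can only reduce the post-baseline cases. A baseline case cannot depend on the assigned arm. The rule is identical across arms, the SAP was prepared before unblinding, and the primary endpoint (EASI75) does not use SCORAD. Each affected subject is worth at most about 0.084 points in an arm mean, assuming 125 per arm and a latent dryness of 3.

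Two limits remain. The frequency of affected records is unknown, and Protocol 14.1 gives no SCORAD effect size, SD or power, so an effect on a test decision can be neither calculated nor shown. Should such records prove common, Protocol 14.3.16 already gives the occasion to notice: "All the analyses specified in the protocol will be reviewed in relation to the blinded data actually obtained".

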### **6.6.4 Multiple imputation**

For the analysis of the primary and secondary endpoints, multiple imputation will be carried out, as specified in the protocol, using SAS PROC MI. Unless otherwise specified in the protocol or this SAP, the seed 11109946 will be used in any multiple imputation strategies.

When performing multiple imputation of continuous parameter values, imputed values outside the relevant parameter scale for visits prior to the relevant visit will be used as it is. Values imputed at the relevant visit will be truncated to the nearest upper or lower bound on the given scale. E.g., negative imputed EASI values at Week 16 will be set to 0 in an analysis of Week 16 data.

#### Secondary endpoints IGA 0/1

For imputation of IGA values, the LIKELIHOOD=AUGMENT option will be used (1).

For imputation of IGA values, it may occur that the observed data from which the imputation model is fitted does not contain all levels of the IGA predictors necessary for the imputation. Imputation will be performed within treatment groups at each visit. E.g. if at a visit within one treatment group, the IGA values (0,1,2,3) for each level have 2 or more observed values but the IGA value of 4 only has 1 or less, the imputation model will not be able to predict for IGA

values of 4 at that specific visit. I.e. categories can be combined at a visit for one group, but not the other. To avoid this situation, in this specific example IGA values of 3 and 4 will be combined into a single category prior to the imputation. In general, if this situation arises, IGA categories will be combined into a single category at the specific visit for the purpose of the imputation, according to the rules in [Table 1](#).

**Table 1: Adjacent IGA categories combined if a predictor contains 1 or less observed values**

IGA value(s) in imputation model	IGA categories combined
0	(0,1)
1	(0,1)
2	(2,3)
3	(2,3)
4	(3,4)

## 6.6.5 Analysis of other endpoints

As specified in the protocol, but with the change that ‘Other’ endpoints will not be analysed for the secondary estimand (‘composite’), but for the tertiary estimand (‘treatment policy’), as originally proposed in previous versions of the protocol.

### Percent change of DLQI

The analyses of percent change in DLQI at Week 16 and Week 26 have been added in support of the secondary endpoints.

### Calculation of Weekly average of Eczema-related Sleep NRS

Weekly averages of Eczema-related Sleep NRS will be calculated using the same rules as for the weekly averages of pruritus NRS. As for the Worst Daily Pruritus NRS, in case there are several Eczema-related Sleep NRS assessments at the same date only the worst will be used.

### HADS

For the analysis of the endpoint HADS-anxiety < 8 and HADS-depression < 8, the imputation of missing data due to the COVID-19 pandemic or set to missing due to the COVID-19

Trial ID: LP0162-1346	Date: 21-OCT-2020	Version: v1.0 Page 17 of 35
-----------------------	--------------------------	--------------------------------

pandemic will be imputed within each sub-score prior to analysis using the primary analysis of the primary estimand.

#### Amount of TCS used

The amount of TCS used will be calculated as specified in section 6.6.8 and analysed in two ways, reflecting the two consumption assumptions. The primary analysis will be using the most conservative assumption that all missing tubes were fully used. The second assumption will be used as a sensitivity analysis, reflecting the primary analysis’s extreme opposite, that all non-returned tubes were not used. The method used for analysis will be the one specified in the protocol. Additionally, descriptive histograms of both consumption assumptions will be produced.

In an extra sensitivity analysis, the amount of TCS used will be log transformed. This transformation has in a similar trial proven to fit data better. TCS amount will be log transformed by adding 1 (due to potential zero values) and then taking the logarithm. The analysis will use the same repeated measures model with the mean modelled as follows:

$$\log[\text{TCS amount used} + 1] (g) = \text{Treatment} * \text{visit} + \text{prior CSA use} + \text{country} + \text{Baseline IGA}$$

The analysis results will be presented by back-transforming using the exponential function, thus producing estimated geometric means and estimated ratio of means, which will be presented with nominal p-values and 95% confidence intervals (CI). This sensitivity analysis will be done for both consumption assumptions.

Additionally, descriptive histograms of both consumption assumptions will be produced for the amount of TCS.

#### Number of days without topical treatment use

The number of days without topical treatment use will be analysed as specified in the protocol. Number of days without topical treatment use will be calculated using the same rules as for the Worst Daily Pruritus NRS (weekly average).

#### Scoring of PROs

**Table 2: Scoring of PROs**

POEM	Scored according to: https://www.nottingham.ac.uk/research/groups/cebd/documents/methodological-resources/poem-for-self-completion.pdf
------	---

Trial ID: LP0162-1346	Date: 21-OCT-2020	Version: v1.0 Page 18 of 35
-----------------------	--------------------------	--------------------------------

DLQI	Scored according to: http://sites.cardiff.ac.uk/dermatology/quality-of-life/dermatology-quality-of-life-index-dlqi/dlqi-instructions-for-use-and-scoring/
EQ-5D-5L	Index values calculated according to: https://euroqol.org/eq-5d-instruments/eq-5d-5l-about/valuation-standard-value-sets/crosswalk-index-value-calculator/ The UK value sets will be used.
HADS	The HADS consists of 14 items, 7 of which are related to anxiety and 7 related to depression. The maximum score is 21 for each subscale (anxiety and depression). If one question is missing within a subscale, the response to that question will be imputed as the mean of the remaining questions in that subscale. If more than one question is missing within a subscale, the subscale is considered missing.
SF-36	Version 2, acute recall.

### 6.6.6 Analysis of patient-reported outcomes

As specified in the protocol.

### 6.6.7 Analysis of exploratory supporting endpoints

As specified in the protocol.

### 6.6.8 Drug accountability

For each subject, the weight of TCS used for a given visit interval (WGTUSED) will be calculated as the difference between the weight of the tubes dispensed (WGTDISP) and the weight of the returned tubes (WGTRET):

- if  $WGTRET \leq WGTDISP$  then  $WGTUSED = WGTDISP - WGTRET$
- if  $WGTRET > WGTDISP$  then  $WGTUSED = 0$ .

When tubes are not returned as specified in the protocol, the following rules will be applied:

- If tubes are returned at the wrong visit, the amount of TCS used from these tubes will be assumed to be used in the period from the tubes being dispensed to being returned.
- If a dispensed tube is not returned at all and the subject remains in the study, two different approaches will be applied to explore two extreme assumptions:
  1. It will be assumed, conservatively, that the missing tube has been fully used by the subject in the period between the date the tube was dispensed, and the date of the

next subsequent visit attended by the subject. Estimated content (100 g) for the kit number will be used as a contribution to the WGTRET.

2. It will be assumed that the missing tube has not been used at all by the subject in the period between the date the tube was dispensed, and the date of the next subsequent visit attended by the subject, i.e. contribution from the tube to the WGTRET is set to 0.
- In the case where tubes from the last dispensing visit are not returned due to the subject being withdrawn from the trial, the amount of TCS used from these tubes will not be calculated (i.e. set to missing).
  - If dispensed tubes have no weighing data due to any other cause the most conservative estimate will be imputed, i.e. that the whole tube dispensed was used.

If a subject does not attend a planned visit, daily usage (DAYUSE) is calculated for the period between the tubes being dispensed and the subsequent dispensing visit, i.e.

$DAYUSE = WGTUSED / DURATION$  where  $DURATION = ENDDATE$  (date of the subsequent dispensing visit) -  $STARTDATE$  (date of the tubes being dispensed). If all tubes in the batch are not dispensed/returned at the same time, date of the first dispensed or last returned tube in the batch is used, dependent on the situation. The amount of the TCS used for each visit in the period (missing visit(s) and the first visit after the tubes being dispensed) is calculated by multiplying daily usage (DAYUSE) by the number of days between the visit and the previous visit.

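### The two runs for unreturned TCS tubes move both arms together, so they are extremes of consumption and not of the treatment difference, and the conservative label is unsupported for that difference

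*SAP*

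**What the plan says.** SAP 6.6.8 sets the rule by subject and visit interval, without reference to arm: "For each subject, the weight of TCS used for a given visit interval (WGTUSED) will be calculated" as dispensed weight minus returned weight, "WGTUSED = WGTDISP - WGTRET", and as zero if the returned weight is the larger.

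For a tube never returned by a subject who stays in the study, "two different approaches will be applied to explore two extreme assumptions":

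- Run 1: "It will be assumed, conservatively, that the missing tube has been fully used by the subject", with the instruction "Estimated content (100 g) for the kit number will be used as a contribution to the WGTRET".
- Run 2: "It will be assumed that the missing tube has not been used at all by the subject", with a contribution of 0 to the same returned weight.

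SAP 6.6.5 (Amount of TCS used) ranks them: "The primary analysis will be using the most conservative assumption that all missing tubes were fully used". The unused run is the sensitivity analysis. A further sensitivity analysis on log(amount + 1) repeats the same two assumptions.

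Tubes without a weight for another reason have a separate rule and no opposite run: "If dispensed tubes have no weighing data due to any other cause the most conservative estimate will be imputed", meaning the whole tube counts as used.

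Protocol Panel 4 states the resource-use objective as a comparison of tralokinumab+TCS with placebo+TCS. Protocol 14.3.10 analyses TCS amount with a repeated measurements model containing treatment by visit.

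**The concern.** Assuming that all lost tubes were emptied raises both arm means, and assuming that none was used lowers both. A between-arm difference responds only to the imbalance in lost tubes. It does not respond to how much cream they held if that is assumed equal in the two arms. Cream use is itself the outcome, so the share used from a lost tube could differ by arm, and no planned run allows for that.

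Two consequences follow. Close agreement between the planned runs may be read as robustness to lost tubes when it shows only that the arms lost similar numbers. And the run labelled most conservative may be the one that shows more TCS sparing.

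**Working it through.** **Inputs.** Tube content is 100 g (SAP 6.6.8). The amount used is dispensed minus returned weight (same section). Loss rates are not given in either document, so those below are assumptions.

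**Step 1: the tube rule as written.** Take two 100 g tubes dispensed (200 g), one returned weighing 40 g and one not returned.

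- Run 1 as written: 200 − (40 + 100) = 60 g. A fully used lost tube should give (100 − 40) + 100 = 160 g.
- Run 2 as written: 200 − (40 + 0) = 160 g. An unused lost tube should give (100 − 40) + 0 = 60 g.

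The formula therefore swaps the two assumptions. Leaving the lost tube out of the dispensed weight does not help: run 1 becomes 100 − 140, set to 0 g, and run 2 becomes 60 g. Text and arithmetic agree if the contribution is made to the used weight instead. The next steps follow the described assumptions, not the returned-weight arithmetic.

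**Step 2: effect on the difference.** For each arm let m be the mean number of unreturned tubes per subject-interval and f the fraction used from such a tube. Let D0 be the difference (tralokinumab minus placebo, g per interval) when lost tubes count as 0 g; a more negative value favours tralokinumab. Then

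D = D0 + 100 × (fT·mT − fP·mP).

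- Planned runs: fT = fP = 1 gives D0 + 100(mT − mP), and fT = fP = 0 gives D0. They are 100·|mT − mP| apart.
- Possible range: from D0 − 100·mP (fT = 0, fP = 1) to D0 + 100·mT (fT = 1, fP = 0), a width of 100(mT + mP).

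**Step 3: numbers, relative to D0.**

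| Assumed mT, mP | Fully used, both arms | Unused, both arms | Possible range | Width |
|---|---|---|---|---|
| 0.10, 0.10 | 0 g | 0 g | −10 to +10 g | 20 g |
| 0.05, 0.15 | −10 g | 0 g | −15 to +5 g | 20 g |
| 0.20, 0.10 | +10 g | 0 g | −10 to +20 g | 30 g |
| 0.20, 0 | +20 g | 0 g | 0 to +20 g | 20 g |

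The planned runs reach both ends of the range only when one arm loses no tubes (last row). The fully used run is the less favourable of the two only when tralokinumab loses more tubes (third row), and there it still falls 10 g short of the worst case.

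**Step 4: what still moves under equal loss.** Only the linear point estimate is fixed.

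- Variance: if 10% of subject-intervals lose one tube, independently of measured use, the fully used run adds 100² × 0.10 × 0.90 = 900 g² to the variance within each arm. The CI and p-value can change.
- Log scale: for amounts of 60 g and 80 g, (60 + 1)/(80 + 1) = 0.75. Adding 100 g to both gives 161/181 = 0.89. The gram difference stays at −20 g but the ratio changes.

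The algebra in step 2 is exact for raw arm means at one interval and approximate for the adjusted repeated measurements model.

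**The case against.** The strongest reply is that the SAP does not claim to bound the treatment difference. It presents two consumption assumptions, and as extremes of consumption from non-returned tubes they are what they say. That stands. The point is narrower: they are the only planned checks on lost tubes for a comparative endpoint, and the conservative label has no support for that comparison.

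A reader might infer that the sensitivity analysis cannot fail, or will show robustness whatever the tubes held. The documents do not support this. Under equal loss the interval, the p-value and the planned log-scale ratio can all change, and under unequal loss the point estimates separate as well.

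A reader might also infer that the SAP promises an opposite extreme for unweighed tubes and does not deliver it. It does not promise one: the opposite run is limited to non-returned tubes. Varying the unweighed tubes would be an addition.

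The rule's reach is limited too. Late returns, and tubes outstanding at withdrawal, have their own rules in SAP 6.6.8. Protocol 14.3.10 excludes data after permanent discontinuation, rescue treatment or subject-onset of the pandemic. The crossed runs assume every lost tube emptied in one arm and untouched in the other, which is a logical limit and not a likely state, so they belong as supplements.

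**Conclusion.** The point holds as a cheap improvement. On the linear scale the planned runs span 100·|mT − mP| g of a possible 100(mT + mP) g, and they fall short of the full range whenever both arms have unreturned tubes. The run called most conservative enlarges the apparent TCS sparing if placebo loses more tubes. Nothing in the documents says that it does, so the supported statement is that the label cannot be justified in advance, not that the primary analysis favours tralokinumab.

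The direction rests on reading the described assumptions over the returned-weight arithmetic. Programmed literally, the labels swap: at 0.05 against 0.15 the nominal primary run would be 10 g less favourable to tralokinumab than the sensitivity run. The shortfall in range is the same either way. The gram figures rest on assumed loss rates.

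The stakes are modest. It would be wrong to treat TCS amount as the sole endpoint for the resource-use objective: Panel 4 also lists days without topical treatment, which come from the eDiary and do not depend on tube returns. Both are 'other' endpoints, and the hierarchy in Protocol 14.3.6 covers only primary and secondary endpoints.

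**What to change.** 1. Correct SAP 6.6.8 first: make the 100 g (fully used) and 0 g (unused) contributions to the used weight, not the returned weight, so that formula and description agree.
2. Keep both planned runs. Add two crossed runs as supplementary bounds: unreturned tubes fully used in tralokinumab+TCS and unused in placebo+TCS, and the reverse. Report the number of unreturned tubes by arm and visit interval.
3. In SAP 6.6.5 and 6.6.8, stop describing full use in both arms as conservative for the treatment difference. Of the four runs, full use in tralokinumab+TCS with no use in placebo+TCS is the least favourable to tralokinumab on the linear scale.
4. Optionally, put tubes with no weighing data through the same runs instead of fixing them at full use.

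The cost is a few sentences of SAP text, two more runs of an existing model, and a wider reported range.

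### SAP 6.6.8 computes the reverse of its two stated assumptions for TCS tubes that are never returned

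*SAP*

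**What the plan says.** SAP 6.6.8 states that the "weight of TCS used for a given visit interval (WGTUSED) will be calculated as the difference between the weight of the tubes dispensed" and the weight of the tubes returned. If the returned weight exceeds the dispensed weight, use is set to 0.

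For a tube that never comes back while the subject remains in the trial, the section gives two rules meant as opposite extremes:

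- **Rule 1** assumes that "the missing tube has been fully used by the subject". Its computing step is: "Estimated content (100 g) for the kit number will be used as a contribution to the WGTRET".
- **Rule 2** assumes that "the missing tube has not been used at all by the subject". Its computing step is: "contribution from the tube to the WGTRET is set to 0".

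SAP 6.6.5 (Amount of TCS used) assigns these to analyses: "The primary analysis will be using the most conservative assumption that all missing tubes were fully used". The sensitivity analysis takes the other extreme, "that all non-returned tubes were not used". A further set of analyses is planned under both assumptions: "In an extra sensitivity analysis, the amount of TCS used will be log transformed". Histograms are also planned for both.

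**The concern.** WGTRET is subtracted. A tube that was emptied should return nothing, so its contribution to WGTRET should be nil. A tube that was not touched should count as returned at full weight. The SAP does the opposite in both rules, so each computing step contradicts the assumption it is meant to carry out.

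If a programmer follows the text, the analysis called primary and conservative credits the lower use to missing tubes, and the sensitivity analysis credits the higher. The log-transformed versions and the histograms inherit this. So does the daily-use figure that 6.6.8 derives from WGTUSED to spread use over missed visits. The phrase about 100 g for the kit number adds a second uncertainty: Protocol 9.1.2 and 9.8.1 give 180–225 g per kit and no weight per tube, so the reader cannot tell whether 100 g is meant per tube or per kit.

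**Working it through.** **Inputs.** From SAP 6.6.8: WGTUSED = max(WGTDISP − WGTRET, 0); contribution of a missing tube to WGTRET of 100 g under rule 1 and 0 g under rule 2. From the protocol: 180–225 g per kit. Assumptions: tube weight *w*, and grams *u* used from a tube that was returned. Tube weights tried are 100 g (the SAP's estimate), 90 g (180/2), 112.5 g (225/2) and 45 g (180/4).

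**One missing tube, counted in WGTDISP.** The SAP's own estimate implies 100 g used under rule 1 and 0 g under rule 2. As written:

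| *w* (g) | Rule 1 (full use): max(*w* − 100, 0) | Rule 2 (no use): *w* − 0 |
|---|---|---|
| 45 | 0 | 45 |
| 90 | 0 | 90 |
| 100 | 0 | 100 |
| 112.5 | 12.5 | 112.5 |

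Rule 1 is below rule 2 in every row, and must be for any *w* > 0.

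**Two tubes, one missing, *u* = 40 g used from the other.** WGTDISP = 2*w*, and the returned tube weighs *w* − *u*.

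- Rule 1 as written: 2*w* − (*w* − *u* + 100) = *w* + *u* − 100.
- Rule 2 as written: 2*w* − (*w* − *u*) = *w* + *u*.
- Intended full use: *w* + *u* with the tube's own weight, or *u* + 100 with the SAP's estimate.
- Intended no use: 2*w* − (*w* − *u* + *w*) = *u*.

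| *w* (g) | Rule 1 as written | Intended full use, own weight (shortfall) | Intended full use, 100 g estimate (shortfall) | Rule 2 as written | Intended no use |
|---|---|---|---|---|---|
| 90 | 30 | 130 (100) | 140 (110) | 130 | 40 |
| 100 | 40 | 140 (100) | 140 (100) | 140 | 40 |
| 112.5 | 52.5 | 152.5 (100) | 140 (87.5) | 152.5 | 40 |

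**Missing tube left out of WGTDISP** (*w* = 100, *u* = 40). Rule 1 gives max(100 − (60 + 100), 0) = 0 g, where 140 g is intended. Rule 2 gives 100 − 60 = 40 g, as intended. This reading repairs rule 2 only.

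**Weights that include packaging** (assumed empty tube 10 g, content 100 g, two tubes, one missing, 30 g used from the other). Rule 1 gives 220 − (80 + 100) = 40 g and rule 2 gives 220 − 80 = 140 g. The intended values are 130 g and 30 g. The reversal remains.

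**Effect on a contrast.** On the raw scale, away from the floor, rule 1 as written is 100 g short per missing tube (own-weight basis) in both arms. The between-arm difference is then biased only if non-return differs: each percentage point of difference in the share of intervals with one missing tube moves the mean difference by 100 × 0.01 = 1 g.

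The shift no longer cancels on the log scale or at the floor. Two single-interval illustrations, each with one missing tube on both sides:

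- Log scale, 100 g tubes, *u* = 40 against 80. As written: log(81) − log(41) = 0.681, ratio 1.98. Intended: log(181) − log(141) = 0.250, ratio 1.28.
- Floor, 90 g tubes, *u* = 5 against 20. As written: max(90 + 5 − 100, 0) = 0 g and 90 + 20 − 100 = 10 g, difference 10 g. Intended: 95 g and 110 g, difference 15 g.

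**The case against.** The best defence is that this is a slip in one variable name. The intended direction is stated in both rules, again in 6.6.5, and again in the last rule of 6.6.8, where a tube without weighing data is treated as wholly used. If WGTRET is read as WGTUSED and the missing tube is left out of WGTDISP, both rules match their labels. The intent is indeed clear. But that reading is itself a correction that the SAP does not make, and it needs two changes: altering the variable while leaving the tube in WGTDISP counts the tube twice.

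A second point is that both extremes are reported, so for 100 g tubes the same pair of results would appear with the labels exchanged. That is true at 100 g. At 90 or 112.5 g the exchange is inexact (30 or 52.5 g instead of 40 g), and in every case the wrong result is called primary.

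Third, the log and floor figures compare two intervals and are not estimates for the trial. This stands. If only one subject in each arm of about 125 (250 randomised 1:1) lost a tube at that visit, the mean log difference would move by (0.681 − 0.250)/125 ≈ 0.003. The size of any trial-level effect depends on a non-return rate that the documents do not give.

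Finally, the scope is narrow. The rule covers only tubes never returned by subjects who remain in the trial; last-dispensed tubes not returned because of withdrawal are set to missing.

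**Conclusion.** The concern holds. Followed as written, each rule gives the opposite of its stated assumption, and no plausible reading of the dispensed weight rescues rule 1. On the own-weight basis the full-use rule falls 100 g short per missing tube when the floor does not apply, and the no-use rule overstates use by the tube's own weight. These sizes rest on assumed tube weights and on the tube being counted as dispensed; the direction does not depend on tube weight.

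The importance is minor to moderate, and it should be fixed. Amount of TCS used is listed under Other endpoints (Protocol Section 6, Panel 4) and lies outside the hierarchy in Protocol 14.3.6, so no confirmatory conclusion depends on it. The harm arises only if the program follows the text, and the program is not available to check.

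**What to change.** Reword the two rules in SAP 6.6.8:

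- Keep the missing tube in WGTDISP at its own dispensed weight. Protocol 9.2.2 has tubes weighed before shipment, so this weight should exist.
- Full use: contribution to WGTRET of 0, or the empty-tube weight if recorded weights include packaging.
- No use: contribution to WGTRET equal to the tube's own dispensed weight.
- State whether 100 g is per tube or per kit. Use it only where a dispensed weight is unavailable, with the same value entered in both WGTDISP and WGTRET.
- Do not add the tube to WGTUSED while it is still in WGTDISP.

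Then check the program against the corrected text. The cost is two lines of SAP wording, a short clarification and a program check; no new data are needed.
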